# IRB Protocol for Human Subjects Research

period of time, the fNIRS imaging system will measure the brain activity of the participant.

- A multimodal Quantitative Sensory Testing (QST) battery will be completed for Conditioned Pain Modulation (CPM). These measures will be assessed using equipment and methods available at [name] laboratory, including a Medoc TSA- II Neurosensory Analyzer, a temperature-controlled pain generator to produce thermal pain stimulation to the most painful knee and ipsilateral forearm and Wagner pressure algometer to produce pressure pain stimulation to the most painful knee and trapezius. We will be applying pressure stimulation combined with the participant holding their hand under cold water for one minute at most.
- Psychosocial symptoms will be measured by FMI (ranges from 14 to 56), COVID-stress scale (range from 0 to 144), CESD (ranges from 0 to 60), and PCS (ranges from 0 to 52). FMI is a 14-item instrument (range, 14 to 56), with higher scores indicating more skill with the mindfulness technique. The FMI has a reported Cronbach's alpha coefficient of 0.86. COVID-stress scale, CESD, and PCS are commonly used in clinical studies.
- We will measure participant satisfaction with treatment using the Client Satisfaction Questionnaire (CSQ-8). The CSQ-8 comprises eight items that are summed to yield an overall score of 8-32, with higher scores indicating greater satisfaction. The CSQ-8 has a reported Cronbach's alpha coefficient of 0.87-0.93. Moreover, we will evaluate the presence and severity of possible side effects of treatment at the end of each session on a 0 (not at all) to 10 (highest degree) scale. The participants will be asked in an open- ended manner whether they experienced any side effects, and they will complete a brief questionnaire assessing side effects that can occur with tDCS or MBM (e.g., itching, headache, fatigue, dizziness). This approach has been used in our previous study and frequently in other studies.

## 10.3 Specify the total estimated time commitment for subject participation, and the estimated time commitment for each activity.

We expect that participants will be in this research study for four months. For a two-week period, participants will perform self-administered tDCS and MBM at their home or private room for eight days (Monday – Friday) of 20-minute supervised Zoom sessions. There will also be three lab visits lasting two hours each within those two weeks: once on the first day, once in the middle of the study, and once during the last day. Should they choose to participate, there will be two visits lasting one hour in the MRI facility, once before the first lab session and once after the last lab session. Finally, we will follow up with participants once a month for three months after the two-week period through phone survey for 20 minutes each or having the participant mail their paper survey answers to the office.

# IRB Protocol for Human Subjects Research

**10.4** If any biological specimens (blood, urine, tissue, etc.) are being collected for research, state the amount (ml/tsps./tbsp, etc.), method, frequency, and type of specimen to be collected and what the specimen will be used for.

N/A

**10.5** If the study is a clinical trial, confirm registration with <https://clinicaltrials.gov/> has been completed:

This study is not a clinical trial:

Registration complete:

Registration pending:

## 11.0 Potential Benefits to Subjects:

**11.1** Describe the anticipated benefits of this study to society, academic knowledge, or both.

The central hypothesis is that remotely supervised tDCS paired with MBM at home will decrease clinical pain and OA-related clinical symptoms, improve physiopsychological pain processing, increase participant satisfaction with treatment, and decrease maladaptive changes in pain-related function. This hypothesis will be tested by pursuing the following specific aims: determine the effects of active tDCS paired with active MBM on clinical pain and OA-related clinical symptoms (specific aim 1); determine the effects of active tDCS paired with active MBM on physiopsychological pain processing (specific aim 2); determine the effects of active tDCS paired with active MBM on participant satisfaction with treatment (specific aim 3). The proposed research is significant because it is expected to provide valuable insight into an exciting new modality of nonpharmacological pain self-management that is extremely easy, safe, and noninvasive with minimal side effects.

**11.2** Describe any benefits that individuals may reasonably expect from participation (not including compensation, which cannot be considered a benefit of participation).

Brain Stimulation and meditation have been shown to reduce pain in some older adults. We cannot promise any benefits to participants in this research. However, this study will help us to understand whether self-brain stimulation and meditation will reduce pain in older adults with knee osteoarthritis, which might lead to better treatment for people with such conditions.

## 12.0 Risks to Subjects:

### 12.1 Describe all physical, psychological, social, legal, and/or economic risks that could be associated with participation in this research.

- MRI. The MRI environment is cramped and may provoke claustrophobia in some subjects. MRIs are associated with repetitive loud noises in the range of 126 – 131 dB on a 3T system. The radio frequency (RF) energy deposited in the body during an MRI scan can increase body temperature. Proximity burns may arise due to deposition of focused RF energy into the body where it touches the bore of the magnet. Known as the projectile effect, the strong magnet field can draw in MR-unsafe objects in a rapid and uncontrolled manner that can pose a serious threat to the health and life of those in the room.

Significant risks may exist for people with:

- Cardiac pacemakers
- Metal clips (stents) on blood vessels
- Artificial heart valves
- Artificial arms, hands, legs, etc.
- Brain stimulator devices
- Implanted drug pumps
- Ear implants & augmentation (e.g. cochlear implants, hearing aids)
- Eye implants, metal fragments in eyes, colored contact lenses
- Exposure to shrapnel or metal filings (e.g. military combat, sheet metal workers, welders)
- Other metallic surgical hardware anywhere in the body or on the skin
- Certain tattoos with metallic ink
- Certain transdermal (skin) patches such as NicoDerm (for tobacco dependence), Transderm Scop (for motion sickness), or Ortho Evra (birth control)

Significant risks can also arise if metallic or magnetic objects and materials are brought into the scanning area (e.g. jewelry, piercings, pocket knife). Such items could get pulled into the magnet at great speed and can cause serious injury.

- tDCS. The Soterix Medical 1x1 tDCS mini-CT Stimulator may cause transient minor irritation, discomfort and redness at the electrode sites. tDCS has not been shown to cause seizures nor lower the seizure threshold in animals. There are no reports of seizure induced by tDCS in human participants in the literature. However, this may not be true for epilepsy patients, whose seizure threshold rates are likely abnormal. Therefore, potential participants who have a history of seizures or epilepsy will be excluded from the study.
- MBM. The risks of MBM are minimal. Occasionally, participants report transient anxiety or mild discomfort during MBM.

# IRB Protocol for Human Subjects Research

- Demographic and clinical survey questionnaires. The potential risk of the questionnaires involves participants' feelings of discomfort or unease when reading or responding to survey questions that are personal.
- Thermal stimulation. The Medoc TSA-II Neurosensory Analyzer will be used to create thermal stimulation, which will use a heating apparatus that has a low risk of burning skin. The TSA-II is covered under FDA 510K #K922052, which has both hardware and software safety limits that will not go beyond a certain temperature limit (50 C) in order to prevent burning of the skin.
- Functional near-infrared spectroscopy. Optical fibers will be secured to the participant's scalp using the cap's grommets. Although there is no designed measure that protects the participants from the risk of discomfort due to prolonged wearing of headgear, we will assess the participants' level of discomfort through direct question immediately after wearing the headgear and periodically during the experiment. Participants will be instructed that they can discontinue the procedure if they experience any discomfort or unpleasant effects.
- Conditioned pain modulation. There are risks of bruising and lingering pain by applying gradual pressure stimuli with the pressure algometer. The participant will tell the examiner as soon as they feel pain or discomfort as pressure gradually increases and the examiner will immediately release pressure. We will be doing the same pressure stimulation combined with the participant holding their hand under cold water for one minute at most. The participant may withdraw their hand from the cold water at any time before the minute elapses if the cold pain is too much to bear.

## 12.2 Discuss what steps will be taken to minimize risks to subjects/data.

- MRI. To mitigate risks, the following steps will be adopted: The protect the hearing of subjects, they will be provided with ear plugs and headphones to lower sound levels to no more than 99 dB(A). Adequate ventilation in the MRI bore and a magnet room temperature of 20°C will be maintained at all times to ensure subjects can maintain body temperature. Blankets will be provided, if necessary. To eliminate the possibility of proximity burns, pads will be used to ensure that the subject's tissues do not directly come into contact with the inner bore of the magnet during the MR imaging process. Also, for this reason, subjects' body tissues will not be permitted to form a conductive loop. Pads will be used to ensure this cannot happen. Any MR-safe or MR-conditional equipment necessary for the conduct of the scan will be introduced into the magnet room before the subject to ensure there is no risk to the health and life of those in the room due to a potential projectile effect. MR-unsafe objects are never allowed in the magnet room. To ensure that subjects can be safely scanned, they will be screened for MRI suitability at least three times: once upon prospective enrollment into the MRI arm of the study, upon enrollment, and finally on the day of the MRI scan.

# IRB Protocol for Human Subjects Research

- **tDCS**. To minimize risk associated with tDCS, participants will be asked to report any discomfort, and the examiner will monitor participants throughout the stimulation sessions. All tDCS sessions will be remotely supervised by a trained experimenter. Participants may stop at any time. tDCS has not been shown to cause seizures nor lower the seizure threshold in animals. There are no reports of seizure induced by tDCS in human participants in the literature. However, this may not be true for epilepsy patients, whose seizure threshold rates are likely abnormal. Thus, history of seizure is an exclusionary criterion for our study.
- **MBM**. Participants will be instructed that they can discontinue the procedure if they experience any discomfort or unpleasant effects.
- **Demographic and clinical survey questionnaires**. Throughout each questionnaire, participants will be reminded that participation is completely voluntary, they can refuse to answer any question, and they can stop at any time. Breaks will be given if needed. Research staff who collect data will have previous training in the conduct of all survey questionnaires.
- **Functional near-infrared spectroscopy**. Although there is no designed measure that protects the participants from the risk of discomfort due to prolonged wearing of headgear, we will assess the participants' level of discomfort through direct question immediately after wearing the headgear and periodically during the experiment. Participants will be instructed that they can discontinue the procedure if they experience any discomfort or unpleasant effects.
- **Thermal stimulation**. The following precautions will be employed in the proposed study: 1) participants will be informed that they can withdraw their arm from the stimulator at any time; 2) the experimenter will continuously monitor stimulus temperature and can manually discontinue stimulation at any point; and 3) the stimulator has a built-in shutdown system to prevent the delivery of prolonged or high-intensity stimuli. Inconvenience to participants will be minimized by delivering brief stimuli that are below the individual's thermal pain tolerance level. The thermal stimulator will start generating heat at the temperature less than human body temperature and participants will be provided with the button to stop the stimulator the moment they feel discomfort or pain. These procedures will ensure maximum patient safety and comfort while allowing successful and reliable imaging of the brain.
- **Conditioned pain modulation**. The risks of bruising and lingering pain will be diminished by applying slow, gradual pressure to the knee and shoulder with the pressure algometer, wherein the participant will tell the researcher to stop the moment they feel discomfort or pain and the researcher will immediately release pressure. The researcher will record the numeric reading on the pressure algometer. We will also be doing the same test while the participant's hand is in ice-cold water. We will let the participant to take their hand out of the cold water at any time it becomes too much within the one-minute time limit and the time of cold withdrawal (in seconds) will be recorded. All the

# IRB Protocol for Human Subjects Research

stimulation and testing sessions will be supervised by trained research staff who will monitor potential adverse effects and symptoms. At each stimulation session, participants will be asked to report any adverse events they have experienced.

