# IRB Protocol for Human Subjects Research

## 10.2 Description of research procedures.

Participants who meet eligibility criteria and give informed consent will be randomly assigned at a ratio of 1:1:1:1 to one of the four groups: (a) active tDCS paired with active MBM (n=50), (b) sham tDCS paired with active MBM (n=50), (c) active tDCS paired with sham MBM (n=50), or (d) sham tDCS paired with sham MBM (n=50) using the order of entrance in the study and previous randomization list generated via SAS software. The randomization will balance the allocation of patients to the study arms with respect to distributions of age, race, and sex. tDCS with a constant current intensity of 2 mA will be applied for 20 minutes per session daily for 2 weeks (Monday to Friday) via the Soterix 1x1 tDCS mini-CT Stimulator device (Soterix Medical Inc., NY; 6.5 inches long, 3 inches wide, 0.7 inches thick) with headgear and 5x7 cm pre-saturated, single use, individually packed sponge electrodes. The FDA has ruled that the aforementioned tDCS stimulator is a “non-significant risk” device, a requirement for Investigational Device Exceptions. The sponge electrodes snap into the custom headgear, which is secured to the participant’s head for simple and fail-safe electrode preparation. This single-position headgear with clearly labeled sponge markers eliminates room for user error and helps conserve accurate and reproducible sponge placement. Participants can only administer a stimulation session via the Soterix 1x1 tDCS mini-CT Stimulator device after being provided a single-use unlock code by the research staff once proper contact quality is achieved (only the on/off button will be adjustable by the study participants; they will not be able to adjust the device settings). After the participant enters the unlock code, the screen on the device will show a timer that counts down the minutes until the end of the session. At 20 minutes, the device will turn off automatically, and study staff will instruct the participant to remove the headset and discard the sponges and to safely store all materials for the next session. For sham stimulation, the electrodes will be placed in the same positions as for active stimulation, but the stimulator will only deliver 2 mA current for 30 seconds. This sham stimulation method has been shown to be reliable and indistinguishable from active treatment. During each tDCS session, participants will practice MBM. The meditation intervention will be applied simultaneously with tDCS for 20 minutes per session daily for 2 weeks by a recorded meditation on a CD. Participants will be provided with a CD player and earphones. The recording will instruct participants to close their eyes, connect to the openness of one’s mind, and mindfully maintain and deepen the connection through breathing with more openness and awareness. The sham MBM intervention will be delivered via a CD player that will look identical in both active and sham MBM. The sham recording will instruct participants to relax and take deep breaths every 3 minutes without the specific mindfulness-based instructions (e.g., practicing mindful attention to the breath in a non-evaluative manner). All other aspects of the sham MBM intervention (e.g., body position, time spent listening to instructions, eyes closed) will match the active MBM.

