# IRB Protocol for Human Subjects Research

†On days 5 and 10, tDCS paired with MBM will be delivered at [name] laboratory, followed by data collection of self-report measures (NRS, WOMAC, FMI, CSQ-8 [only day 10]), and immediately afterwards, the fNIRS and CPM will be collected.

- MRI. MRI will be completed within a week from the baseline visit and the last visit. Scans will be conducted at the Translational Bioimaging Resource (TBIR) located in UA. Only FDA-approved MRI devices will be used.
- MMSE. MMSE will be used to exclude people with diminished cognitive function (i.e., Mini-Mental Status Exam score  $\leq 23$ ).
- Kellgren-Lawrence Scores. Kellgren-Lawrence scores collected from existing patient x-rays will be conveyed from [name] to the research study team. If available, we will collect Kellgren-Lawrence Scores or x-rays directly from non-Banner affiliated participants. The scores will be used in the study to determine OA severity.
- Medical History Questionnaire. All participants will complete a thorough questionnaire to collect demographic and medical history details, including age, sex, height, weight, duration of knee OA, current and past treatments for knee OA, comorbid conditions, and current medications.
- Clinical pain intensity will be measured by asking participants to rate their average knee pain over the past 24 hours via NRS from 0 (no pain) to 100 (worst pain imaginable). Following the Initiative on Methods, Measurement, and Pain Assessment in Clinical Trials recommendations for clinical trials involving chronic pain, pain intensity changes assessed through an NRS will be our primary outcome measure for data analysis purposes.
- We will measure OA-related clinical symptoms using Western Ontario and McMaster Universities Osteoarthritis Index (WOMAC), which ranges from 0 to 96, with higher scores indicating worse OA pain-related symptoms.

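### No adverse-event question is described after the day-10 visit, so delayed effects of the day-10 pain tests, and events at the second MRI or during follow-up, depend on spontaneous report

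*Combined protocol and SAP*

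**What the plan says.** Two places in the protocol say when participants are asked about harms. The conditioned pain modulation (CPM) item of section 12.2 ends: "At each stimulation session, participants will be asked to report any adverse events they have experienced". The satisfaction item of section 10.2 says "we will evaluate the presence and severity of possible side effects of treatment at the end of each session", using an open question and a brief questionnaire about effects of tDCS or MBM.

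Treatment runs on weekdays for two weeks, so the tenth and last session is day 10. The footnote to the schedule table in section 10.2 gives the order on days 5 and 10: treatment, then self-report measures, and "immediately afterwards, the fNIRS and CPM will be collected". Section 10.3 places the two MRI visits "once before the first lab session and once after the last lab session", and section 10.2 puts the second scan within a week of the last visit. Follow-up is monthly for three months, by a 20-minute phone survey or a mailed paper survey (section 10.3).

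Section 12.1 names harms that can show or persist after a visit. For CPM it says: "There are risks of bruising and lingering pain by applying gradual pressure stimuli with the pressure algometer". It also lists a low risk of thermode burns, and proximity burns from MRI.

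Three other passages bear on the point:
- The sentence just before the first quote says that all "stimulation and testing sessions will be supervised by trained research staff who will monitor potential adverse effects and symptoms".
- Headgear discomfort during fNIRS is assessed "through direct question immediately after wearing the headgear and periodically during the experiment" (sections 12.1 and 12.2).
- The prompt in section 15.3 asks for a timeline of safety data collection. The answer describes the Safety Monitoring Committee, its annual meetings and its adjudication of events as needed. It gives no timeline.

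**The concern.** Asking at each session works as long as another session follows. Bruising after the baseline or day-5 tests can be reported at the next session. After day 10 there is no next session, yet the third set of pain tests, the second scan and three months of follow-up are still to come or are only just finishing.

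At stake is the meaning of the safety record. Up to day 10 it holds answers to a direct question. After day 10 it holds only what participants volunteer. The two periods cannot be read in the same way, and an empty table after day 10 would not show that nothing happened. The Committee reviews what reaches it and is not itself a means of collecting events.

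**Working it through.** No power or error-rate calculation applies. The check is a count of contacts, matching each to any adverse-event question that the text describes.

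**Step 1. Number of sessions.** Eight home sessions (section 10.3) plus two laboratory sessions on days 5 and 10 (section 10.2) give 8 + 2 = 10. The payment rule in section 13.1 agrees: 10 × $10 + 3 visits × $30 + 3 follow-ups × $10 = $220, the stated maximum. Day 10 is therefore the last session.

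**Step 2. What each contact can pick up.**

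| Contact or procedure | Question on the day | Later question for delayed effects |
|---|---|---|
| Baseline tests, first MRI | Staff monitoring of testing sessions; headgear question in fNIRS | Yes, at later sessions |
| Day-5 tests | As above, plus the session question | Yes, at sessions 6 to 10 |
| Day-10 tests | As above, plus the session question | None described |
| Second MRI | None described | None described |
| 1-, 2- and 3-month contacts | None described | None described |

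After the day-10 visit an MRI participant has 1 + 3 = 4 planned contacts, and none has a described adverse-event question. Without MRI it is 0 of 3.

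**Step 3. Does the result depend on the meaning of stimulation session?** The term is not defined. If it means a tDCS session, the last is day 10. If it means pain stimulation, as its place in the CPM item might suggest, the last is also day 10. The session in section 10.2 is likewise undefined. If it means the whole visit, the day-10 question moves to after the tests, but still to the same day. Nothing is asked later on any of these readings.

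**Step 4. Length of the period without a described question.**
- On the protocol's own figures: 3 months of follow-up / 4 months of participation = 75%.
- In days, assuming a 91-day follow-up, 12 days from the first to the last session inclusive, and the 3- to 7-day lead-in of section 10.2: 91 / (91 + 12 + 3) = 91/106 = 86%, and 91 / (91 + 12 + 7) = 91/110 = 83%.

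The 75% is used below because it rests on stated figures and is the lower value.

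**Step 5. How many participants a change can reach.** Section 6.3 gives 28 (treatment and MRI) + 8 (treatment only) = 36 participants to be recruited locally. Fewer can be reached if some have already finished follow-up.

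**The case against.** The strongest reply is that safety is watched more closely than the collection rule alone suggests. Trained staff monitor testing sessions as well as stimulation sessions, headgear discomfort is asked about directly, and participants tell staff to stop as soon as they feel discomfort. A reader might infer that harms from the day-10 tests are never asked about or noticed. The documents do not support that: effects on the day are observed and partly asked about. What remains is effects that appear after the participant has left.

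A reader might also point to the schedule table, which has no adverse-event row at follow-up. It has none on treatment days either, although the text says side effects are collected then. Its silence is weak evidence, and the point rests on the text.

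Third, side effects of the treatment itself are sought at the end of every session. The tests and scans are assessments given irrespective of arm, and the collection rule is the same in all four arms. A reader might infer a biased comparison between arms, but nothing in the documents shows one. Likewise, the wording in section 11.1 about a safe treatment with minimal side effects is an expectation, not a planned safety conclusion.

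Fourth, other routes exist. Section 15.2 refers to an operating procedure for adverse events and to a physician and the principal investigator reachable by phone during procedures. Section 14.1 refers to manuals of procedures. These were not supplied and might define a collection window. The monthly scales would also show persistent knee pain in part. This stands as a limit on the point. It does not fill the gap in the protocol, because section 15.3 is where the timeline was requested.

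**Conclusion.** The point holds for delayed and later events. As written, delayed effects of the day-10 tests, events at the second MRI, and events in the three months of follow-up depend on spontaneous report. That is about 75% of the stated four months, with no question described at any of the four later contacts (three without MRI).

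The 75% is a share of calendar time, not of risk, since all ten treatment sessions fall in the covered part. A reader might scale the gap to the full planned enrolment. The documents do not support that as the effect of a change made now, because data from earlier sites are only being compiled and those sites' adverse-event procedures are not described. The practical reach is at most 36 participants, 28 with MRI.

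The conclusion assumes that the unsupplied operating procedure and manuals do not already schedule a later question. If they do, the protocol needs only to say so. Otherwise this is a worthwhile and inexpensive improvement to safety ascertainment. It does not affect the efficacy analysis.

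**What to change.** In sections 10.2 and 15.3:

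1. Add the existing open adverse-event question and brief side-effect questionnaire to the 1-, 2- and 3-month contacts, in both the phone and the mailed versions. The first contact should ask specifically about the day-10 testing and, where it applies, the second MRI.
2. Ask the open question at the close of the day-10 testing and at the close of each MRI visit.
3. State the collection period in section 15.3, and include these data in the reports to the Safety Monitoring Committee.

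The cost is a short amendment and a few minutes at contacts that already take place, with no new visit or staff. There are two limits. Day-10 effects would be recalled after up to a month, which is why the question at the close of testing is also needed, although that question cannot catch what appears later. Participants already through follow-up will lack the items, so safety tables must state which period is covered for whom.
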